### **2.1.3 Dose Escalation**

Dose escalation in the SRD part under fasting conditions

#### 2.1.4 Food effect part

Since a [redacted] of BI 705564 at higher doses might be improved by the application of food, the effect of food on the relative bioavailability of BI 705564, as tablet formulation will be investigated. The food effect may be dose dependent.

#### 2.1.5 Conclusion

The safe starting dose in this study is determined [redacted] This dose is not expected to trigger any relevant or unacceptable biological activities.

In the single rising dose part under fasting conditions, the following dose escalation scheme is planned:

Each dose escalation step in the single rising dose part under fasting conditions will be guided by interim PK measurements and projected exposure levels.

With global amendment No 4, a single rising dose part under fed conditions is added.

[redacted] Each dose escalation step in the single rising dose part under fed conditions will be guided by interim PK measurements and projected exposure levels.

## 2.2 TRIAL OBJECTIVES

The primary objective of the single rising dose parts under fasting and under fed conditions is to investigate safety and tolerability of BI 705564 in healthy male subjects following oral administration of single rising doses. Secondary objectives are the exploration of

pharmacokinetics (PK) including dose proportionality, and pharmacodynamics (PD) of BI 705564 after single rising doses.

The objective of the food effect part is to explore the relative bioavailability of BI 705564 tablets under fed and fasting conditions following the oral administration of single doses.

A description of the endpoints to be determined, and the observations along with specific information as how to collect the data, is provided in [Section 5](#).

## 2.3 BENEFIT - RISK ASSESSMENT

Participation in this study is without any (therapeutic) benefit for healthy subjects. Their participation in the study, however, is of major importance to the development of this compound which is expected to be superior over other BTK inhibitors being developed in non-oncological indications due to its higher selectivity. Subjects participating in this trial are exposed to the risks of study procedures and those, related to the exposure of trial medication.

### 2.3.1 Procedure-related risks

The use of an indwelling venous catheter for the purpose of blood sampling may be accompanied by mild bruising and also, in rare cases, by transient inflammation of the wall of the vein. In addition, in rare cases, a nerve might be injured while inserting the venous catheter, potentially resulting in paresthesia, reduced sensibility, and/or pain for an indefinite period. Same risks apply to venipuncture for blood sampling.

The total volume of blood withdrawn during the entire study per subject will not exceed the volume of a normal blood donation, i.e. 500 mL. No health-related risk to healthy subjects is expected from this blood withdrawal.

### 2.3.2 Drug-related risks and safety measures

Factors of risk may derive from particular knowledge or the lack thereof, regarding (1) the mode of action, (2) the nature of the target, (3) the relevance of animal models and/or (4) findings in non-clinical safety studies.

#### 2.3.2.1 Mode of action

BTK is a well characterized target with known functions in the immune signalling pathways of B cells and myeloid cell lineages (see [Section 1.1](#)). First clinical experience with the approved BTK inhibitor ibrutinib is available (see [Sections 1.1](#) and [1.2.5](#)). In addition, a 'human model' with loss of function mutations of the BTK gene is known as syndrome XLA. The immunodeficiency of XLA patients seems to be limited to the decreased levels of circulating antibodies. The resulting (predominant) bacterial infections should be well controlled by the application of antibiotics and gammaglobulin substitution, if necessary [[R17-0404](#)].

Ibrutinib treatment in patients with hematologic malignancies is associated with adverse events including hypertension, thrombocytopenia, and GI complaints (abdominal pain,

nausea, diarrhea, and vomiting). As these are not usual features of XLA, they may be related to off-target inhibition by ibrutinib of other enzymes besides BTK. Atrial fibrillation has been reported in patients receiving ibrutinib. The causal relationship of this finding to ibrutinib is not clear. The majority of affected patients had pre-existing cardiovascular disease, and most cases resolved quickly [R17-0124]. Other investigational BTK inhibitors (GDC-0853 and CC-292) were generally well tolerated in Phase 1 and Phase 2 clinical trials in healthy volunteers and in patients with rheumatoid arthritis. Serious infections, hypertension, thrombocytopenia, and atrial fibrillation were not reported [R17-0165, R17-0166]. All these conditions can be well monitored and are accessible to established therapies.

BI 705564

(see Section 1.2.1).

will be the minimum time between treatments in the food effect part (wash-out period) and from last administration of study drug until the end of trial examination in all study parts.

#### 2.3.2.2 Nature of the target

The BTK protein is intra-cellular expressed in myeloid and lymphoid cell lines, predominantly in the immune system (bone marrow, appendix, lymph nodes, tonsils, and spleen), as well as in the lung. [R17-0406] Although on-target effects are unlikely to occur after a single dose of BI 705564, they might resemble those seen in XLA patients: Inhibition of B-cell differentiation which may manifest as a transient decrease of peripheral B-cell numbers, transient decrease of immunoglobulin levels and unlikely bacterial infections. Main safety measures performed throughout the study will be therefore: (1) Exclusion of subjects with a repeated decrease of CD19+ B cell count at screening. (2) Monitoring of white blood cell counts and particularly CD19+ B cell counts, as well as immunoglobulin levels for at least 10 days after drug administration. (3) Close monitoring for adverse events including symptoms of infections. (4) In case of infections, appropriate clinical evaluation and, if necessary, adequate treatment thereof.

'Down-stream' effects of BTK inhibition are well characterized (see Section 1.2.1). How these effects may vary in different populations, e.g. healthy subjects versus diseased patients, young versus elderly, different patient populations, etc., is not known. Also, no information on BTK polymorphisms in healthy individuals and their potential influence on pharmacodynamics effects of BI 705564 or other BTK inhibitors are available.

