**(2) Food effect part**

Visit	Day	Planned time (relative to drug administration) [h:min]	Approximate clock time of actual day [h:min]	Event and comment	Safety laboratory	PK  blood	12-lead ECG	Vital signs (BP, PR)	Questioning for AEs and concomitant therapy 
1	-21 to -1			Screening (SCR) 	x		x 	x	
2/ 3*	-3 to -1	-72:00 	08:00	Ambulatory visit	x				x
	1	-2:00	06:00	Admission to trial site  , allocation to treatment  (Visit 2 only)	x 	x 	x 	x 	x 
		-0:30	07:30	High fat, high calorie breakfast (only in treatment 'fed')					
		0:00	08:00	Drug administration					
		0:30	08:30			x			
		1:00	09:00			x	x 	x	x
		1:30	09:30			x			
		2:00	10:00	240 mL fluid intake		x	x 	x	x
		3:00	11:00			x			
		4:00	12:00	240 mL fluid intake, thereafter lunch 		x	x 	x	x
		6:00	14:00			x			x
		8:00	16:00	Snack (voluntary) 		x	x 	x	x
		10:00	18:00			x			
		11:00	19:00	Dinner					
		12:00	20:00			x			x
	2	24:00	08:00	Discharge from trial site, breakfast  (voluntary)	x	x	x 	x	x
		34:00	18:00	Ambulatory visit		x			x
	3	48:00	08:00	Ambulatory visit		x			x
	4	72:00	08:00	Ambulatory visit		x			x
4	11 to 15			End of trial (EOT) examination 	x		x 	x	x

\* Two identical visits, separated by a wash-out interval of at least 10 days between drug administrations

1. Subject must be informed and written informed consent obtained prior to starting any screening procedures. Screening procedures include physical examination, check of vital signs, ECG, safety laboratory (including drug screening), demographics (including determination of body height and weight, smoking status and alcohol history), relevant medical history, concomitant therapy and review of inclusion/exclusion criteria. Pharmacogenetic samples will be collected, if needed.
2. The time is approximate. The respective procedure is to be performed and completed within 3 h prior to drug administration. Allocation to treatment may be performed at any time following enrolment but must be completed prior to the first drug administration.
3. If several actions are indicated at the same time point, the intake of meals will be the last action.

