4. End of trial examination includes physical examination, vital signs, ECG, safety laboratory, recording of AEs and concomitant therapies.
5. Only urine drug screening and alcohol breath test
6. AEs and concomitant therapies will be recorded throughout the trial, but will be specifically asked for at the time points indicated in the Flow Chart.
7. The ECG will be recorded as single ECG. However, the number of ECGs per time point may be increased to three ECGs based on the preliminary ECG results obtained during the single rising dose part.
8. Sampling times may be adapted based on information obtained during the trial (e.g. preliminary PK data) including addition of samples and visits as long as the total blood volume taken does not exceed 500 mL per subject.
9. Safety laboratory to be taken and medically evaluated within 3 days prior to administration of study drug. This ambulatory visit, including safety laboratory, can be omitted in visit 2, if the screening examination is performed on Days -3, -2 or -1.

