- If one dose level is safe and shows acceptable tolerability, and if no stopping criterion is met (see [Section 3.3.4.2](#)), the next higher dose may be given, keeping a minimum dosing time interval of 10 days between the first subject of the current dose group and the first subject of the following dose group.
- Extensive standard safety laboratory measurements including serum electrolytes, serum amylase and lipase, differential white blood counts, as well as CD19+ B cell and platelet counts will be performed before and after study drug administration (see [Flow Charts](#) and [Section 5.2.3](#)).
- A thorough ECG and heart rate monitoring will be performed, including continuous ECG measurements over 4 hours post dose to cover the anticipated period of highest drug exposure, and additional repeated single 12-lead ECGs.
- Prior to each dose escalation, a documented safety review will be performed by the Principal Investigator (or an authorized deputy) and the Trial Clinical Monitor (or an authorized deputy). For details, see [Section 3.1](#).
- In the food effect part, the 10 mg dose will be tested first and thereafter the 40 mg dose will be tested\*. The 10 mg dose will only be given, if, in the single rising dose part, doses of up to 40 mg are safe and of acceptable tolerability. The 40 mg dose will only be given, if, in the single rising dose part, doses of up to 160 mg are safe and of acceptable tolerability and, if, based on available preliminary PK data, the systemic exposure (group gMean  $C_{max}$ ,  $AUC_{0-24}$ ) is not expected to exceed the maximal group gMean values reached in the single rising dose part\*.

\* [Global Amendment No 4](#): In the food effect part, the 40 mg dose is not tested.

- Subjects will be confined under close observation for at least 24 hours after drug administration at the trial site and will be discharged only after a formal assessment and confirmation of fitness by an investigator or qualified designee. During in-house confinement subjects will be under medical observation and thoroughly monitored for both, expected and unexpected adverse events.

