### 5.2.3 Assessment of safety laboratory parameters

For the assessment of laboratory parameters, blood and urine samples will be collected by the trial site at the time points indicated in the [Flow Charts](#) after the subjects have fasted for at least 10 h. Overnight fasting is not required at the discretion of the investigator or designee for retests or drug screening. In the single rising dose part under fed conditions, fasting is not applicable to the post-dose safety laboratory on Day 1.

The parameters that will be determined are listed in Tables 5.2.3: 1 and [5.2.3: 2](#). Reference ranges will be provided in the ISF, Section 10.

Manual differential white blood cell count or urine sediment examinations will only be performed, if there is an abnormality in the automatic blood cell count or in the urinalysis, respectively.

Table 5.2.3: 1 Routine laboratory tests

Functional lab group	Test name	SCR	A 	B 	C 	EOT
Haematology	Haematocrit	x	x	x	x	x
	Haemoglobin	x	x	x	x	x
	Red blood cell count (RBC)	x	x	x	x	x
	Reticulocyte count	x	--	--	x	x
	White blood cell count (WBC)	x	x	x	x	x
	Platelet count	x	x	x	x	x
Automatic WBC differential (relative and absolute)	Neutrophils, eosinophils, basophils, monocytes, lymphocytes	x	x	x	x	x
Manual differential WBC (if automatic differential WBC is abnormal)	Polymorphnuclear neutrophils (segs), band neutrophils (stabs), eosinophils, basophils, monocytes, lymphocytes					
Lymphocyte differentiation (relative and absolute; except for ratio)	T cells (CD3+), T helper cells (CD3+CD4+), cytotoxic T cells (CD3+CD8+), B cells (CD19+), natural killer cells (CD16+CD56+CD3-), double-positive T cells (CD3+CD4+CD8+), CD4:CD8 ratio	x	--	--	x 	x
Serum immunoglobulins	IgA	x	--	--	x	x
	IgG	x	--	--	x	x
	IgM	x	--	--	x	x
Coagulation	Activated partial thromboplastin time (aPTT)	x	x	x	x	x
	Prothrombin time (Quick's test and INR)	x	x	x	x	x
	Fibrinogen	x	--	x	x	x

 A: Days -3 to -1

 B: post-dose on Day 1 (single rising dose parts)

 C: Days 2, 3, 8 (single rising dose parts) and Day 2 (food effect part)

 Not on Day 3 (single rising dose parts)

Table 5.2.3: 1 Routine laboratory tests (cont'd)

Functional lab group	Test name	SCR	A 	B 	C 	EOT
Enzymes	Aspartate transaminase (AST/GOT)	x	x	x	x	x
	Alanine transaminase (ALT/GPT)	x	x	x	x	x
	Alkaline phosphatase (AP)	x	--	x	x	x

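### In the food effect part, CD19+ B cells and immunoglobulins are followed for only 24 h after dose 1 before dose 2 is given, although Section 2.3.2.2 states at least 10 days of monitoring after drug administration

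*Protocol*

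**What the plan says.** Protocol Section 2.3.2.2 discusses possible on-target effects of BTK inhibition and introduces its list of precautions with "Main safety measures performed throughout the study will be therefore". The second item is monitoring of white blood cell counts, "particularly CD19+ B cell counts, as well as immunoglobulin levels for at least 10 days after drug administration". No study part is excepted.

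Table 5.2.3: 1 (Section 5.2.3) marks lymphocyte differentiation, which contains the CD19+ count, and IgA, IgG and IgM at screening, column C and end of trial. Columns A (Days -3 to -1) and B (Day 1 post-dose) carry a dash for both groups. The footnote defining column C reads "C: Days 2, 3, 8 (single rising dose parts) and Day 2 (food effect part".

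Flow Chart 2 describes the two crossover periods as "Two identical visits, separated by a wash-out interval of at least 10 days between drug administrations", followed by one end of trial examination on Days 11 to 15. Its footnote for Day 1 before dosing limits the laboratory work to "Only urine drug screening and alcohol breath test", and Table 5.2.3: 1 has no Day 1 pre-dose column.

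SAP Section 6.7 sets one laboratory baseline, the last measurement before the first dose of the first period. For vital signs it uses a separate baseline in each period. Protocol Section 7.3.4 assigns each measurement to the actual treatment at its planned time and plans an evaluation of laboratory differences from baseline.

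**The concern.** The text in Section 2.3.2.2 and the schedule that a site would follow do not agree for the first of the two food effect doses. A decrease in CD19+ cells or immunoglobulins that appeared, or persisted, later than 24 h after dose 1 would not be seen before the subject was dosed again.

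There is also an interpretive cost. The period 2 values are assigned to the second treatment, but they are compared with a value from before dose 1. Any residual effect of dose 1 is then counted with dose 2. Because the two doses differ in food condition, fed and fasting cannot be separated in those values either.

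**Working it through.** No power or error-rate formula applies. The check crosses the columns of Table 5.2.3: 1 with the visits of Flow Chart 2.

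**Inputs.** Wash-out W of at least 10 days (240 h) between doses; column A on Days -3 to -1; column C on Day 2 (24 h) in the food effect part; end of trial on Days 11 to 15, which is 10 to 14 days after the last dose; screening on Days -21 to -1; pre-dose procedures within 3 h before dosing.

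**The stated 10 days, where they reproduce.** In the rising dose parts, CD19+ falls on Days 2 and 8 and at end of trial, so 1, 7 and 10 to 14 days after the dose. Immunoglobulins are also measured on Day 3, at 2 days. Food effect dose 2 has values at 1 day and at 10 to 14 days. The stated minimum is reached in both cases.

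**Food effect dose 1, in hours from dose 1 at W = 240 h:**

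| Occasion | Time (h) | CD19+ and immunoglobulins |
|---|---|---|
| Screening | -504 to -24 | yes |
| Visit 2, Days -3 to -1 | -72 to -24 | no |
| Visit 2, Day 2 | 24 | yes |
| Visit 3, Days -3 to -1 | 168 to 216 | no |
| Visit 3, Day 1 pre-dose | 237 to 240 | no |
| Dose 2 | 240 | |
| Visit 3, Day 2 | 240 + 24 = 264 | yes |
| End of trial | 240 + 240 = 480 to 240 + 336 = 576 | yes |

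- Last value after dose 1 and before dose 2: 24 h, against at least 240 h stated.
- Age of that value when dose 2 is given: 240 - 24 = 216 h, or 9 days.
- Gap between consecutive values: 264 - 24 = 240 h. It equals the wash-out, so it would be 288 h at 12 days and 336 h at 14 days (both assumed for illustration).

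**What a period 2 change contains.** Since column A has no such tests, the SAP baseline for them is the screening value. The Visit 3 Day 2 change from baseline is then

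effect of dose 2 at 24 h + residual effect of dose 1 at W + 1 days + drift since screening.

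At the minimum wash-out, the time from screening to that sample is between 1 + 10 + 1 = 12 and 21 + 10 + 1 = 32 days. No sample in the period 2 pre-dose window allows the second and third terms to be removed. The period 1 values at 24 h do not have this problem.

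**The case against.** The best defence is literal. Section 2.3.2.2 gives a duration; it does not give a sampling frequency or require an interval free of further dosing. A completer is sampled until end of trial, which at the minimum wash-out is 480 to 576 h, or 20 to 24 days, after dose 1. On that reading 10 days are covered. This stands as a reading of the sentence. It does not restore monitoring of dose 1, because every value after 24 h also follows dose 2.

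Several stronger inferences are tempting, and the documents do not support them:

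- A reader might infer that the protocol expects a B cell fall. Section 2.3.2.2 calls on-target effects unlikely after a single dose and describes any decrease as transient.
- A reader might infer that the objective of this part is missed. Its objective is relative bioavailability (Section 2.2); safety is additional and descriptive (Section 7.1.1).
- A reader might infer that re-exposure is unmonitored. White cell count with automatic differential and platelets are in column A, and the allowance to omit that visit applies to Visit 2 only.
- A reader might see a second contradiction in Section 2.3.2.7, where tests "as well as CD19+ B cell and platelet counts will be performed before and after study drug administration". Screening and post-dose values satisfy that wording.

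The defence can also say that SAP Section 7.8.2 mainly compares laboratory values with reference ranges, which needs no period baseline. That is fair for the listings. It does not cover the differences from baseline planned in Protocol Section 7.3.4, which SAP Section 4 says will be performed with the other planned analyses.

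**Conclusion.** The inconsistency is real but narrow. For lymphocyte subsets including CD19+, and for IgA/IgG/IgM, the food effect schedule gives 1 day of follow-up after dose 1 before re-exposure, against at least 10 days stated. There is no value in the period 2 pre-dose window. It affects all 12 planned subjects of this part who go on to dose 2. The rising dose parts and food effect dose 2 reach the stated duration, and the bioavailability analysis is untouched.

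The conclusion assumes that the 10 days apply to each administration; the text makes no exception but does not say so expressly. It also assumes that Table 5.2.3: 1 and Flow Chart 2 hold the full schedule for these tests. The reasoning for the wash-out in Section 2.3.2.1 is partly blacked out, so the likelihood of carry-over cannot be judged. An end of trial examination for a subject who stops after period 1 does not help completers.

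**What to change.** Reconcile Section 2.3.2.2 with Table 5.2.3: 1 and Flow Chart 2. Which route applies depends on whether sampling is still possible: the Amendment 4 note in Section 3 already reports 10 mg food effect data but does not say whether that part is complete.

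**If sampling is still possible**, a change to measurements only would be to add lymphocyte differentiation and IgA/IgG/IgM before dose 2, at one or both of:

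- the safety blood already drawn at Visit 3, Days -3 to -1, which is evaluated before dosing but at the minimum wash-out falls 7 to 9 days after dose 1;
- the Day 1 pre-dose PK venepuncture, at about 10 days, though possibly up to 3 h short (240 - 3 = 237 h).

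Amend SAP Section 6.7 so that this value is the period 2 baseline for these tests. If one occasion is used, the cost is two assay groups once per subject (12 subjects) and a few mL of blood within the 500 mL limit, plus table, flow chart and SAP edits. No extra visit is needed.

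**If the part is complete**, limit the scope of Section 2.3.2.2 to the rising dose parts and food effect dose 2. State in the SAP and trial report that period 2 changes in CD19+ and immunoglobulins cannot be separated between doses or between fed and fasting. This costs text only.

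No dosing or stopping rule is proposed.

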#### 2.3.2.3 Relevance of animal species and models

Animal models and assays, used during the pharmacological (mice) and toxicological (rats, dogs) assessment of BI 705564 were similar, at large, to those used for the development and submission of ibrutinib. As such, their relevance for humans was acknowledged by regulatory authorities [R17-0403]. For further information, see current version of IB [c12104992-02].

#### 2.3.2.4 Findings in non-clinical safety studies

Documents supporting the submission of this first-in-man trial with BI 705564 were compiled according to Good Clinical Practice (GCP) principles. All pivotal, non-clinical safety studies in support of this clinical trial were conducted in compliance with Good Laboratory Practice (GLP). For further information, see current version of IB [[c12104992-02](#)].

- Toxicology

In the 4-week rat toxicity study (see [Section 1.2.3.2](#)), laboratory monitoring will include this parameter during the conduct of the study (see [Flow Charts](#) and [Section 5.2.3](#)).

In the same study, dose independent,

(see [Flow Charts](#) and [Section 5.2.3](#)).

In the 4-week dog toxicity study (see [Section 1.2.3.2](#)),

#### 2.3.2.5 Risks resulting from trial medication auxiliaries

Hydroxypropyl- $\beta$ (HP- $\beta$ )-cyclodextrin is a standard excipient in pharmaceutical preparations and is used also in marketed products. The toxicological profile of HP- $\beta$ -cyclodextrin has been thoroughly investigated [[R01-0682](#)]. Orally administered cyclodextrin is practically non-toxic due to lack of absorption from the GI tract. Chronic administration of 16-24 g HP-

$\beta$ -cyclodextrin to healthy volunteers for 14 days led to an increased incidence of soft stool and diarrhoea.

In the current trial, HP- $\beta$ -cyclodextrin is the main ingredient of the solvent for oral solution.

